In sum, as the COVID-19 pandemic continues to ravage US SNFs, novel strategies that maximize the safety and quality of life for SNF residents with ADRD and staff who care for them are urgently needed. To our knowledge, no SNFs have utilized a combined COVID-19 PCR/serology (antibody) testing-based strategy to dictate resident-staff assignments to decrease risk of exposure from COVID-19. Blood samples to obtain serology status and emerging saliva-based PCR tests also have the potential advantage of being less burdensome to obtain than nasal swabs from ADRD patients.

Despite the evolving landscape in nursing homes with the arrival of COVID-19 vaccines, the objective is to continue to pilot test an intervention that leverages COVID-19 and PCR status to pair SNF staff with residents in the safest way possible. However, with vaccination, serologic tests may be less meaningful as either may afford adequate protection. For that reason, we will only seek serology from individuals with no vaccination or no confirmed prior COVID-19 infection. If an individual has received the COVID-19 vaccine, we will not seek serologic testing because a negative test does not indicate a lack of protection. (Current commercially available serologic testing does not detect antibody formation derived from being vaccinated.) Specifically, we propose to pair residents and staff based on the following three conditions: 1) completed vaccination; 2) prior COVID-19 PCR positive testing; and 3) positive serology, if available. We will pair COVID-19 negative residents with antibody-positive/PCR-negative staff and COVID-19 antibody-positive/PCR-negative residents with antibody-negative/PCR negative staff. For our pairing strategy, having a completed vaccination is equivalent to prior positive PCR or positive serology. The main clinical outcome of this novel staff-assignment strategy will be a reduced COVID-19 incidence rate compared to SNF units not using this approach. The pilot project will be done in two facilities with high minority and ADRD representation—Terrence Cardinal Cooke and Mary Manning Walsh of New York City, NY. To ensure the highest likelihood of successful implementation, we propose a phased approach to this research, reflected in following three specific aims:

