This study is innovative for several reasons: 1) a resident-staff cohorting strategy based on a) completed vaccination; b) prior COVID-19 PCR positive testing; and c) positive serology has to our knowledge, never been utilized for infection control in any healthcare setting; 2) although stakeholder-influenced study designs have been increasingly utilized, employing a multi-stakeholder approach to design a facility-specific testing and cohorting strategy is highly innovative and ensures a greater engagement and fidelity across all involved sectors; 3) a detailed implementation design to capture values, changing attitudes, structural and cultural barriers to a testing and cohorting strategy is also innovative and will greatly serve larger trials and best practice disseminations; 4) comparing primary outcomes and infection rates between those with and without ADRD is novel; and 5) the use of smartphone based technology to facilitate proper cohorting while increasing fidelity is highly innovative and ensures greater capture of deviations from the intended approach. Additionally, this approach can benefit facilities in their effort to increase contact-monitoring amongst staff and residents.

D. METHODS AND APPROACH

D.1. Overview: This one-year cluster-randomized pilot study will be conducted in three phases. We have engaged two NYC facilities as the sites of the proposed study, where (Phase 1: AIM 1 – one month) we will convene all stakeholders (leadership, staff, residents, and their families) and engage a panel of experts to create a feasible, scientifically sound protocols for staff-resident assignments based on serology (if applicable), vaccination and PCR testing protocols, and Implementation monitoring. In the second phase (Aim 2 – two months), we will identify four units (average 40 residents per unit) in each facility. We will stratify the two NHs and then within each SNF, randomly allocate two units to the intervention arm and two units to the control arm (we have confirmed homogeneity across these four units in each SNF supporting no need for further stratification). We will conduct baseline serology and/or PCR COVID-19 tests from residents and staff on all four units in each SNF.

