In phase 3 (Aim 3 – six months), we will introduce the staffing assignments based on 1) completed vaccination; 2) prior COVID-19 PCR positive testing; and/or 3) positive serology in the two intervention units, while in control units will employ usual staffing assignments currently in practice in the facilities and only introduce the “concept of” a cohorting strategy. COVID-19 PCR testing will occur in all eight units with a regular frequency (testing frequency changes based on government guidelines) and whenever an individual is symptomatic. The primary outcome will be incidence of COVID-19 infection in residents and as secondary outcomes will include the incidence of COVID-19 infections in staff and hospital transfers due to COVID-19-related symptoms among residents. Implementation assessment will include: 1) proportion of designated staff assignments achieved and reasons for successes and failures; and 2) intervention acceptability using exit stakeholder interviews, with a focus on the experience of ADRD residents. Although the analyses will compare intervention and control units on the primary outcomes of infection incidence and hospitalization, we do not anticipate either event rate to be large enough to reach statistical significance at traditional levels of probability. As real-world management of COVID-19 is rapidly changing, we anticipate that the protocol will continue to evolve over time in terms of testing frequencies and the capacity to assign residents and staff consistent with our strategies. The protocol will be flexible to accommodate such changes. For example, both facilities are launching a SNF-wide resident testing strategy and are responsive to federal testing guidelines. Should a reliable PCR test emerge that is less invasive than the nasopharyngeal swab, we will adopt it into our protocol. Currently no staff member who tests positive

for COVID-19 is allowed to work. Thus, staff-resident assignments will be based on 1) completed vaccination; 2) prior COVID-19 PCR positive testing; and 3) positive serology (when possible) among staff and residents.

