for obtaining qualitative data are implementation-specific and not exploratory, strategies used in exploratory work are germane to this work including the use of open-ended questions and thematic analytic approaches. These methods increase the yield of valuable and actionable information where the interviewer or interviewee has incomplete knowledge, which is required for establishing most feasible and effective strategies. These methods also ensure greater democratization of knowledge and establish a collaborative spirit embodied in respect, mutual cooperation, and trust, all of which will be critical to success especially during these times of strong emotions and potentially grave consequences. We will audio record where permissible and regardless of that determination, we will take detailed notes. In addition to documenting key decisions, we believe that some of the deliberations will reveal and highlight key perspectives and sensitivities that will need to be considered and will inform not only this strategy but future SNF-level intervention strategies that require an abrupt departure from usual practice.

D.3.b. Expert Panel Meetings: We will convene a Panel of Experts familiar with the NH environment that will include two industry leaders, an infection disease specialist, a dementia expert, health equity expert, and a bioethicist. The bioethicist, dementia expert, and health equity expert will be drawn from the Cores and Teams of the IMPACT Collaboratory. We will meet with our Expert Panel prior to study initiation and quarterly over the year of study.

D.4. Methods for Aim 2:

Aim 2: *Employ a protocol based on 1) completed vaccination; 2) prior COVID-19 PCR positive testing; and 3) positive serology (if applicable) in each of the two SNFs among staff and residents to establish their baseline status and three and six months later using on-going surveillance testing.*

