D.5.a. Randomization of Units: 40-bed facility units are the unit of randomization and we will randomize within individual SNFs to select each intervention unit. Should we identify specific unit-level characteristics that are not consistent across units (we have been assured there are none) and may influence our outcomes (such as median age, other demographics or unit size) we will conduct a stratified randomization. We recognize there may be some contamination between staff/residents between intervention/control units but will do our best and monitor this “contamination” as one of our implementation fidelity outcomes.

D.5.b. Staff-Resident Assignment Strategy: Within individual intervention units, we will pair care-partners (staff) with individual residents, based on 1) completed vaccination; 2) prior COVID-19 PCR positive testing; and 3) positive serology (if applicable). For serology testing, antibody negative will be paired with antibody positive as well as antibody-positive with anti-body positive if the frequency of antibody-positive residents and staff is high. Prior known COVID-19 infection and recovery in the absence of vaccination will still require serology testing as we do not yet know how to anticipate antibody development and resilience. Contact between two or more antibody-negative and unvaccinated individuals (and no history of positive PCR) will be restricted such that no antibody negative, unvaccinated individual (and no history of positive PCR) will intentionally interact with another antibody-negative, unvaccinated person (and no history of positive PCR), regardless of individual type (resident or staff). We anticipate that high staffing ratios (more residents with fewer staff) that require the responsibility of one staff person to care for several residents will present considerable challenges to achieving full fidelity, particularly on overnight shifts. Although strict cohorting is a primary implementation goal, we anticipate less than perfect fidelity. Nonetheless, we believe that any reduction in unnecessary exposure will reduce the risk of disease transmission and may lead to meaningful outcomes. Ensuring greatest fidelity will require full engagement of clinical leaders (nursing leads) at the unit level but these leaders will require real-time data for making staffing decisions. These data should also be available to front-line staff so that there is less opportunity for misinformation or lack of information to inform decisions.

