E.1. Quantitative Analyses: The ultimate goal of developing a serologic strategy is to reduce COVID-19 infection rates and hospitalizations. In this pilot phase, where the focus is informing the design of a larger pragmatic RCT, a key focus will be on the ability to measure the outcomes, incident cases of COVID-19 and hospitalizations, in a pragmatic way using administrative data only. Once we have successfully collected these data, we will estimate incident rate ratios using Bayesian Poisson models that include resident length of stay in the nursing home. The Bayesian model provides a posterior probability distribution of the effect of serologic strategy on incidence and hospitalizations. A strength of this analytic approach is that we will be able to conduct ongoing interim analyses to understand if and how the strategy is working as we conduct the study.

The COVID-19 analysis will be conducted at the level of the nursing home unit using this model:

$$Y_i \sim \text{Poisson}(\lambda_i)$$

$$\log(\lambda_i) = \beta_0 + \beta_1 T_i + \log(R_i)$$

Y_i is the number of incident cases for nursing home unit i , $i \in [1, 2, \dots, 8]$. T_i is an intervention indicator, $T_i = 1$ if unit i is using the serologic strategy, $T_i = 0$ otherwise. R_i is the total number resident-days for unit over the 6-month observation period. The parameter λ_i represents the modeled mean for site, and λ_i/R_i is the incidence rate, represented as the number of infections per resident-day. β_1 is the effect of interest: the incidence rate ratio. We will assume an uninformative prior distribution for β_1 . The model for hospitalizations will be developed in the same manner. Both analyses will be conducted using the latest version of R, which is currently 4.0.0 (R Foundation for Statistical Computing, Vienna, Austria).

E.2. Qualitative Analyses: Overview of Qualitative Methodology: This project includes qualitative data from key stakeholder meetings and interviews about: 1) perceptions of the testing program and implementation strategies; 2) perceptions about staff-resident assignment strategies; 3) barriers/facilitators toward program implementation and sustainability including the impact of staffing changes on resident behaviors for those with ADRD. Because much of this work is implementation and feasibility-specific, meetings will often be both information giving and soliciting of other details, e.g., how is testing being conducted currently. We will use focus

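### The primary model omits baseline protection status, which the plan already collects in both arms; adjusting would remove a small chance error (about 1–5% excess variance at 7–14 assumed cases), not a bias

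*Combined protocol and SAP*

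**What the plan says.** Section E.1 models unit counts as Poisson, with log λ_i = β0 + β1·T_i + log R_i over eight units. R_i "is the total number resident-days for unit over the 6-month observation period". No other term appears.

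Protection status is the plan's own classification. Section A defines it by completed vaccination, prior positive PCR or positive serology, and says that for pairing "having a completed vaccination is equivalent to prior positive PCR or positive serology". Section D.5.b adds: "Prior known COVID-19 infection and recovery in the absence of vaccination will still require serology testing".

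The status is collected in both arms. Section D.1 says: "We will conduct baseline serology and/or PCR COVID-19 tests from residents and staff on all four units in each SNF". Aim 2 (section D.4) applies the status protocol "among staff and residents to establish their baseline status and three and six months later using on-going surveillance testing". Section D.4.a holds results per resident, labelled by facility and unit. The overview in section E puts incident infections and serology in the same REDCap tool.

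On balance between arms, section D.1 will, "within each SNF, randomly allocate two units to the intervention arm and two units to the control arm", and states that the units within each facility are homogeneous. Section D.5.a has a fallback: "Should we identify specific unit-level characteristics that are not consistent across units (we have been assured there are none"), randomisation will be stratified. Its examples are age, other demographics and unit size; protection status is not named.

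On event counts, section E expects incidence to be low, and section D.1 says "we do not anticipate either event rate to be large enough to reach statistical significance at traditional levels of probability".

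**The concern.** The plan sorts residents by how likely they are to be infected, records the result before the intervention starts, and then leaves it out of the outcome model. Allocation within facility balances differences between the two facilities. It does not remove chance differences among the four units of one facility, and no model term takes them up.

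The single realised rate ratio can therefore move for a reason that the data could account for. For example, suppose 35% of residents are unprotected in one arm and 25% in the other, and protected residents have 20% of the unprotected risk. With no intervention effect, the crude ratio is then (0.35 + 0.65×0.2)/(0.25 + 0.75×0.2) = 0.48/0.40 = 1.20. At 50% residual risk it is 0.675/0.625 = 1.08. A pilot meant to inform a larger trial should not carry such a shift unexamined.

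**Working it through.** **Inputs.** From the documents: eight units averaging 40 residents (320 in all), two against two within each facility, six months. Assumed, because the documents give no values: unprotected share q = 0.30, residual risk in protected residents r = 0.20, true ratio 1, independent infections, and 7, 14 or 42 cases (2.2%, 4.4% or 13.1% of 320). The plan states no case count, power or variance, so there is no figure of its own to reproduce.

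**Chance imbalance.** With unit-share SD s, the arm difference has SD s×√(1/4 + 1/4).
- Binomial chance only: s = √(0.3×0.7/40) = 0.072, so the difference has SD 0.0512.
- Units differing somewhat more (s = 0.10): SD 0.0707.

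A gap of 10 points or more then occurs in about 5% and 16% of allocations.

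**Effect on the log rate ratio.** The mean relative risk is 0.3 + 0.7×0.2 = 0.44. The added SD is 0.8×0.0512/0.44 = 0.093, or 0.8×0.0707/0.44 = 0.129. The added variances are 0.0087 and 0.0165.

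**Against Poisson noise, about 4/E.** This is 0.571, 0.286 and 0.095 at 7, 14 and 42 cases. The ratios are 1.5%, 3.0% and 9.1% (binomial chance), and 2.9%, 5.8% and 17% (s = 0.10).

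**Simulation.** At most one infection per resident; status-split Poisson fit with a Normal(0, SD 2) prior on status. The cells give the SD of the log ratio, crude v adjusted, and then (crude/adjusted)² − 1.

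| Cases | Binomial chance only | s = 0.10 |
|---|---|---|
| 7 | 0.785 v 0.781: 1.0% | 0.785 v 0.778: 1.8% |
| 14 | 0.589 v 0.581: 2.8% | 0.600 v 0.586: 4.8% |
| 42 | 0.299 v 0.283: 11.6% | 0.313 v 0.284: 21% |

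Drawing cases from a Poisson distribution, as the plan's model does, gives 9% and 16% at 42 cases. Hence about 1–5% at 7–14 cases and 9–21% at 42.

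**Outbreak clustering.** With a unit log-rate SD of 0.5 and s = 0.10, the SDs are 0.497 v 0.480 at 42 cases (7.2%) and 0.730 v 0.718 at 14 (3.4%); at 7 cases the gain is 1.7%. With SD 1.0 the gain is about 1–3% at 42 cases and 0.4–1.6% at 7–14.

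**Other sensitivities.**
- If protected residents have half the risk: 3–5% at 62 cases, about 1% at 21.
- If 10% of statuses are wrong: 21% falls to 14%.
- With s = 0.15 at 42 cases: (0.348/0.288)² − 1 = 46%.
- Over a wider grid without clustering (q 0.1–0.5, r 0.1–0.4, extra between-unit SD 0–10 points), the change runs from a 1.4% increase to a 24% reduction in variance at 7–14 cases, and from a 1.4% to a 53% reduction at 42.

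**Interval.** The mean model SE hardly moves: 0.314 v 0.315 at 42 cases, 0.575 v 0.576 at 14, 0.844 v 0.846 at 7.

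**A wrong way to adjust.** Adding each unit's proportion unprotected to the eight-row model raises the variance by about 57–61% at 7 cases and 24–31% at 14. At 42 it ranges from 13% worse to 19% better.

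**The case against.** The strongest case is that nothing is wrong with the plan. Units are randomised, so the crude ratio is valid, and adjustment is an efficiency choice. The pilot's focus is on whether outcomes can be measured, and it disclaims significance. At 7–14 cases the Poisson 95% limits lie a factor of 4.4 to 2.9 either side, so a 1–5% change in variance would go unnoticed. Forty-two cases would mean about 42/320/0.44 = 30% of unprotected residents infected in six months, which sits poorly with low expected incidence. The protective effect is also unsettled: sections B and D.5.b say that reinfection and antibody persistence are not understood. Finally, resident-level linkage costs effort in a pilot that stresses administrative data.

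Most of this stands, and it sets the priority. It does not remove the point: the status is already held per resident in both arms, and neither the stated homogeneity nor the stratification fallback names it.

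A reader might infer more than the documents support:
- *The rate ratio is biased.* It is not; chance imbalance after randomisation is random error.
- *The resident-day denominator is wrong.* Total resident-days is legitimate; only the status term is absent.
- *Adjustment would tighten the interval or improve coverage.* The model SE does not change. In the simulation at 42 cases, crude coverage is 95.9% (s = 0.10) and 93.6% (s = 0.15), nearer to 95% than the adjusted 97.6% and 97.5%.

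**Conclusion.** The omission is real and the improvement is minor. The planned analysis is valid, but it leaves a small avoidable random error in the point estimate.

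Under the stated assumptions (30% unprotected, 20% residual risk, independent infections), the crude variance exceeds the adjusted variance by about 1–5% at 7–14 cases. The figure of about 9–21% needs about 42 cases and should not be read as the expected gain. Clustering by unit, which is plausible for COVID-19, cuts the two ranges to about 0.4–3% and 1–7%. None of the epidemiological inputs comes from the documents, and the result moves with each of them, upward if units differ more or protection is stronger. The simulation fixed each resident's status for six months, so turnover and new vaccination could shrink the gain.

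A reader might also take a status term as the answer to outbreak clustering. It is not: the model's lack of a unit-level variance term is a separate matter that this leaves untouched.

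**What to change.** Low priority. Aggregate cases and resident-days by unit and baseline status (16 rows, up to 24 with an unknown level). Fit log λ_is = b0 + b1·T_i + b2·Unprotected_s (+ b3·Unknown_s) + log R_is, with a weakly informative prior such as Normal(0, SD 2) on b2 and b3. Report the crude ratio and the rate in each stratum alongside. Do not put the unit proportion protected into the eight-row model.

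State one status rule for both arms, using records dated before the intervention starts, and status at entry for later admissions. Section D.4.a treats residents moving into an intervention unit as COVID-19 negative by default; keep that default out of the analysis. Sections A and D.5.b differ on prior infection without vaccination and must be reconciled before status is coded.

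**Cost.** SAP wording and one or two coefficients. The real work is joining status to cases and resident-days with equal completeness in control units, because section D.4.a names weekly data-quality meetings only for the intervention units. Consent for serology is still open (section D.4.b), so some statuses may be unknown. If unknowns were pooled with unprotected residents and differed between arms, the adjusted ratio would be biased. With 0% v 10% unknown, the pooled level in the second arm is 0.37 of residents at mean relative risk (0.30 + 0.07×0.2)/0.37 = 0.85 instead of 1, and a true ratio of 1.00 becomes about 1.12. With 0% v 20% it becomes roughly 1.24. Kept as a separate level, it stays at 1.00.
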